All analyses were performed in the intention-to-treat population and as superiority analyses. Two-sided p-values of 0.05 or less were considered to indicate statistical significance and associations and effect estimates will be reported with 95% probability symmetric confidence interval (2.5% to 97.5% quantile).

Practical considerations

Data were collected using REDCap (2, 3) hosted by OPEN (Open Patient data Explorative Network, Odense University Hospital, Odense Denmark) with project number OP_530. Data were analyzed using Stata (4) on OPEN's secure analysis server (OPEN Analyse). A prespecified random seed of 7042021 will be used for bootstrapping and imputation.

Planned analyses for primary publication: Change in AVC score

Exclusion criteria

Participants with AVC < 300 at baseline will be excluded from all analyses in this publication.

Outcomes

Primary outcome: Main analysis

The primary outcome was the change in aortic valve calcification (AVC) score (numerical) from baseline to 24 month for the full cohort of included patients.

Secondary outcomes to be included in the primary publication

Secondary outcomes were

- Change in AVC from baseline to 24 months in two prespecified subgroups (baseline AVC score 300-599 and ≥600).
- Change in AVC from baseline to 12 months and from 12 months to 24 months, both for the full cohort as well as for the two subgroups.
- Changes in aortic valve area from baseline to 24 months (numerical)
- Change in peak aortic-jet velocity from baseline to 24 months (numerical)
- Need of heart valve surgery (dichotomous, occurred / not occurred between baseline and 24 months)

- Change in MGP with different phosphorylation and carboxylation forms (numerical)
- Change in QoL from baseline to 24 months (numerical)

Safety outcomes

Safety outcomes were

- Death (all cause and cardivascular cause) (dichotomous)
- Cardiovascular events (a composite endpoint of myocardial infarction, coronary revascularization, stroke, aortic disease, significant peripheral artery disease (surgery), as well as these endpoints separately) (all dichotomous)
- Progressive aortic valve disease (more than 50% increase in AVC score) (dichotomous)
- Venous thromboembolism (dichotomous)
- Severe bleeding
- Low energy or spontaneous fracture
- Cancer (recurrent cancer or new cancer) (dichotomous)

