AVA (Figure 3A) and Vmax (Figure 3B) at baseline, 12, and, 24 months will be presented at line graph for the two treatment groups presenting mean with 95% confidence interval (as obtained from the linear mixed models applied for Table 3). (See mockup figures below)

[figure not shown]
[figure not shown]

Figure 4. Forest plot of stratified analyses of the primary outcome

Coefficients with 95% confidence intervals from stratified analyses (as reported in Table 4) for differences in primary outcome (change of AVA score from baseline to 24 months) between treatment groups will be presented as a forest plot. (See mockup figure below.)

Planned analyses for secondary publication: Change in aortic calcification and diameter

Exclusion criteria

Participants with prior aortic surgery are excluded from this study.

Outcomes

Primary outcome

- Co-primary outcome 1: change in aortic calcification score (numerical) from baseline to 24 month.
- Co-primary outcome 2: change in aortic dilatation (numerical) from baseline to 24 month.

Secondary outcomes

- Change in aortic calcification score from baseline to 12 months and from 12 months to 24 months.
- Change in aortic diameter from baseline to 12 months and from 12 months to 24 months.
- Need of aortic surgery (dichotomous, occurred / not occurred between baseline and 24 months).

Planned tables and figures and corresponding analyses

Table 1. Characteristics of patients at baseline

Statistical methods applied for table 1 are similar to the statistics used for table 1 in the primary publication.

Characteristic	Vitamin K +D group (N=XX)	Placebo group (N=XX)	P-value
Age – years [numerical]			
Baseline aortic calcification score – AU			
[numerical]			
Ascending			
• Arcus			
Descending			
Suprarenal			
Infrarenal			
Renal artery			
Iliaca com artery			
Iliaca ext artery			
Baseline aortic diameter – mm [numerical]			
Ascending			
• Arcus			
Descending			
Infrarenal			
Estimated GFR – ml/min/1.73 m ² [numerical]			·
Body-mass index [numerical]			

dp-ucMGP – pmol/L	
Systolic Blood pressure – mmHg [numerical]	
Smoking	
Active smokers - no (%)	
Former smokers – no (%)	
Non-smokers – no (%)	
Coexisting condition – no (%)	
Hypertension	
Diabetes	
Ischemic heart disease	
Atrial fibrillation	
Renal failure (eGFR<60)	
Medications – no (%)	
ACE inhibitor or ARB	
Beta-blocker	
Mineralocorticoid-receptor antagonist	
Antiplatelet therapy	
NOAC	
Statin therapy	

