		Number	Number	Odds ratio (95	P-
		(proportion)	(proportion)	% CI)	value
Compliance of at least 9	0%				
		Mean change	Mean change	Treatment	P-
		from baseline	from baseline (95	effect (95 % CI)	value
		(95 % CI)	% CI)		
Primary outcome (only i	ncluding with co	mpliance of at least	90%)		
Aortic calcification	0 – 24				
score	months				
 Ascending 					
• Arcus					
 Descending 					
 Suprarenal 					
 Infrarenal 					
Renal artery					
Iliaca com artery					
Iliaca ext artery					
Aortic diameter	0 – 24				
Ascending	months				
• Arcus					
Descending					
Infrarenal					

Figure 1. Enrollment and Randomization of Patients.

Flow chart

[figure not shown]

Figure 2A-H. Aortic calcification according to treatment allocation.

Aortic calcification score at baseline, 12, and, 24 months will be presented at line graph for the two treatment groups presenting mean with 95% confidence interval (as obtained from the linear mixed models applied for Table 2) for each of the 8 aortic calcification outcomes as Figures 2A to 2I. (See mockup figure 2A below, 2B-I similar)

[figure not shown]
[figure not shown]

Figure 3A-D. Aortic diameter according to treatment allocation.

Aortic diameter at baseline, 12, and, 24 months will be presented at line graph for the two treatment groups presenting mean with 95% confidence interval (as obtained from the linear mixed models applied for Table 2) for each of the 4 aortic diameter outcomes as Figures 3A to 3D. (See mockup figure 3A below, 3B-D similar)

Planned analyses for secondary publication: Change in coronary artery calcification and plaque composition

Exclusion criteria

Participants with known cardiovascular disease (CVD) defined as previous acute myocardial infarction (AMI), percutaneous coronary intervention (PCI) and coronary artery bypass graft (CABG) surgery will be excluded.

Outcomes

Primary outcome

The primary outcome in this substudy is the change in coronary artery calcification (CAC) score (Agatston Units) assessed by non-contrast cardiac CT scans from baseline to 24 months follow-up and will be analyzed as continuous variable in the entire population.

Secondary outcomes

The secondary outcomes are as follows:

- Change in CAC score from baseline to 24 months in two prespecified subgroups (baseline CAC score
 <400 and ≥ 400) (numerical)
- Change in CAC score from baseline to 12 months and from 12 to 24 months, both for the full cohort as well as for the two subgroups (numerical)

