Participants with CAC score ≥ 400	Vitamin K+D group	Placebo group	Group difference	
AU	Mean change from baseline (95 % CI)	Mean change from baseline (95 % CI)	Treatment effect (95 % CI)	P-value
Plaque volume and	d composition	1 (55 % 5.)	l	
Total plaque (mm³)				
Calcified plaque (mm³)				
Noncalcified plaque (mm³)				

Low-attenuation		
noncalcified		
plaque (<30 HU)		
(mm³)		
Plaque burden		
T		
Total plaque		
burden (%)		
Calcified plaque		
(%)		
Noncalcified		
plaque (%)		
Low-attenuation		
noncalcified		
plaque (<30 HU)		
(%)		

Figure 1. Enrolment and Randomization of Patients.

* Excluded due to known CVD, including MI, PCI and CABG procedure

[figure not shown]

Figure 2. CAC score progression according to treatment allocation.

CAC score at baseline, 12, and 24 months will be presented as line graph for the two treatment groups presenting mean with 95% confidence interval (as obtained from the linear mixed models applied for Table 3). Moreover it will be presented for the two subgroups (CAC score < 400 and ≥400 AU). (See mockup figure 2A below, 2B and 2C are similar)

[figure not shown]

Figure 3. Change in plaque volume from baseline to 24 months

Change in plaque volume (mm³) with the 4 groups (total, calcified, noncalcified, low-attenuation noncalcified plaque) from baseline to 24 months follow-up will be presented as a box plot to show difference between the treatment group and placebo group.

[figure not shown]
[figure not shown]

Figure 4. Forest plot of stratified analyses of the primary outcome

Coefficients with 95% confidence intervals from stratified analyses (as reported in Table 4) for differences in primary outcome (change of CAC score from baseline to 24 months) between treatment groups will be presented as a forest plot. (See mockup figure below.)

Planned analyses for secondary publication: Changes in volumetric bone mineral density in the lumbar spine and total hip

Exclusion criteria

Participants with use of prednisolone, anti-osteoporotic drugs, and patients with metabolic bone diseases (such as: prostate cancer, bone metastatic cancers, myelotomies, rheumatoid arthritis, primary hyperparathyroidism), patient with immobilization during observation will be excluded.

Outcomes

Primary outcome

- Co-primary outcome 1: change in BMD in spine from baseline to 24 month (numerical)
- Co-primary outcome 1: change in BMD in hip from baseline to 24 month (numerical)

Secondary outcomes

The secondary outcomes are as follows:

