Cortical area	0 – 24 months				
femoral neck					

Cortical area inter- trochanteric regions	0 – 24 months					
Cortical area sub-	0 – 24 months					
trochancheric						
regions						
Bone microstructure (cm)					
Cortical thickness	0 – 24 months					
sub-trochancheric						
regions						
Cortical thickness	0 – 24 months					
femoral neck						
Cortical thickness	0 – 24 months					
inter-trochanteric						
regions						
Cortical thickness	0 – 24 months					
sub-trochancheric						
regions						
Estimated bone strength						
CSMi (cm4)	0 – 24 months					
Section Modulus	0 – 24 months					
(cm3)						

Supplementary Table S1. Sensitivity analysis: Primary outcome with imputation

If more than 5% of observations are missing at 24 months for the main analysis of the primary outcomes reported in Table 2 the analysis will be repeated using multiple imputation (assuming missing at random) by linear regression with all baseline characteristics included in Table 1 as covariates generating 100 imputation sets. Results will be reported in a table structured as Table 2.

Supplementary Table S2. Main analyses adjusted for baseline characteristics

Main analysis as included in Table 2 will be repeated adjusted for D vitamin level and calcium intake at baseline as numerical covariates. The adjusted results will reported in a table structured as Table 2.

Supplementary Table S3. Mean and standard deviation of outcomes at baseline and 24 months

Mean and standard deviation (SD) for all outcomes stratified by treatment group will be reported at baseline and at 24 months.

	Baseline		24 months		
	Vitamin K +D Placebo group		Vitamin K +D	Placebo group	
	group		group		
	Mean (SD)	Mean (SD)	Mean (SD)	Mean (SD)	
Primary outcomes					
Volumetric BMD in					
spine					

Volumetric BMD in			
hip			
Secondary outcome	S		
Volumetric bone mi	neral density (mg/cm3	3)	
Trabeculært vBMD			
total hip			
Trabeculært vBMD			
femoral neck			
Trabeculært vBMD			
inter-trochanteric			
regions			
Trabeculært vBMD			
sub-trochancheric			
regions			
Cortical vBMD			
total hip			
Cortical vBMD			
femoral neck			
Cortical vBMD			
inter-trochanteric			
regions			
Cortical vBMD			
sub-trochancheric			
regions			
Bone geometry (cm2	2)		
Trabecular area			
sub-trochancheric			
regions			
Trabecular area			
femoral neck			
Trabecular area			
inter-trochanteric			
regions			
Trabecular area			
sub-trochancheric			
regions			
Cortical area sub-			
trochancheric			
regions			
Cortical area			

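### The bone publication drops patients immobilised during follow-up, contrary to the SAP's intention-to-treat statement, and gives no time point for its other exclusions

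*SAP*

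**What the plan says.** Under Statistical principles the SAP states, with no exception: "All analyses were performed in the intention-to-treat population and as superiority analyses".

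The Exclusion criteria of the bone publication (volumetric BMD in the lumbar spine and total hip) are one sentence. It opens with "Participants with use of prednisolone, anti-osteoporotic drugs, and patients with metabolic bone diseases", gives examples of those diseases, and ends with "patient with immobilization during observation will be excluded". Immobilisation is not defined, and no time point is given for the drugs or diseases. The co-primary outcomes are the changes in spine and hip BMD from baseline to 24 months. The text for Table 2 says that baseline is measured before randomisation.

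The other three publications fix their exclusions before treatment:

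- Primary (AVC): "Participants with AVC < 300 at baseline will be excluded from all analyses in this publication".
- Aortic: "Participants with prior aortic surgery are excluded from this study".
- Coronary: known cardiovascular disease, meaning an earlier infarction, PCI or CABG.

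The bone section plans three supplementary tables: S1 (multiple imputation if more than 5% of 24-month observations are missing), S2 ("Main analysis as included in Table 2 will be repeated adjusted for D vitamin level and calcium intake at baseline as numerical covariates") and S3 (means and SDs by arm).

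**The concern.** Excluding patients on a characteristic fixed before allocation narrows the population but leaves the randomised comparison intact within it. Excluding them on something that happens during treatment does not, because treatment may influence who is removed. Writing the rule down in advance does not cure this.

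A path from treatment to exclusion is plausible on the SAP's own terms. The publication tests for an effect on bone, and low-energy or spontaneous fracture, which can lead to immobilisation, is a listed safety outcome of the trial. If the active arm had fewer such events, the exclusion would remove more poor bone outcomes from placebo and understate a benefit. If the active arm had more, the exclusion would flatter it.

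The rule is also loosely fixed. Without a definition of immobilisation, or a date for the drug and disease criteria, two analysts could build different populations for the same co-primary tests.

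**Working it through.** **1. The text.** The analysis population is stated as intention-to-treat for all analyses. The bone outcome runs from a pre-randomisation baseline to 24 months, so the observation period is follow-up. Whether a patient meets the immobilisation criterion is therefore settled after allocation. Both statements cannot hold for Table 2 of the bone publication. S1 imputes missing values, S2 adds two baseline covariates and S3 is descriptive; none brings removed patients back.

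**2. Size.** The SAP has no figure to reproduce here: it gives no BMD effect, SD or event rate. Every input below is an assumption except the 400 planned patients and 1:1 allocation (Sample size considerations; Randomizations). Units are SDs of BMD change.

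*Standard error of the arm difference*, taking 200 per arm before exclusions and missing scans: √(2/200) = 0.10 SD.

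*Model A: immobilisation worsens bone.* If immobilised patients do worse by s, removing them shifts the arm difference by (placebo rate − active rate) × s. With s = 0.5 to 1.0:

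| Active v placebo rate | Shift (SD) |
|---|---|
| 5% v 5% | 0 |
| 3% v 5% | 0.02 × s = 0.010 to 0.020 |
| 2% v 5% | 0.03 × s = 0.015 to 0.030 |
| 5% v 10% | 0.05 × s = 0.025 to 0.050 |

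*Model B: exclusion depends on bone change.* BMD change x is N(0.3, 1) on active and N(0, 1) on placebo, with P(excluded | x) = expit(logit(p) − x), so the odds of exclusion rise e-fold per SD of bone loss. Numerical integration gives:

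| p | Excluded, active v placebo | Retained difference | Share of 0.3 | Bias toward zero |
|---|---|---|---|---|
| 0.03 | 3.46% v 4.55% | 0.2900 | 0.967 | 0.010 |
| 0.05 | 5.60% v 7.27% | 0.2852 | 0.951 | 0.015 |
| 0.08 | 8.63% v 11.04% | 0.2795 | 0.932 | 0.021 |

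With a true effect of 0 and the same p in both arms, the bias is 0.

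*Extreme form of B.* Remove everyone below the placebo 3% or 5% quantile. The active arm then loses 1.46% or 2.59%, and the means of the truncated normals differ by 0.033 or 0.047 SD less than the true 0.3.

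*Opposite direction.* Suppose there is no BMD effect but treatment raises the excluded event. Setting p = 0.05 v 0.03 (active v placebo) excludes 7.27% v 4.55% and produces a spurious +0.024 SD in favour of treatment. Setting p = 0.08 v 0.05 excludes 11.04% v 7.27% and produces +0.032 SD. Swapping the arms reverses the signs.

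**3. Against the standard error.** The non-zero shifts run from 0.010/0.10 = 0.1 to 0.050/0.10 = 0.5 standard errors.

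**The case against.** Several points can fairly be made for the plan.

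- **The likely bias is small.** Every rate above is assumed, the bias is zero unless treatment affects bone or an excluded event, and exclusions and missing scans would raise the standard error and so lower the ratio. This stands, and it limits how much weight the point carries. It does not remove the contradiction.
- **The drug and disease exclusions are naturally read as baseline status.** The follow-up wording is attached directly only to immobilisation. This also stands: that part is an ambiguity needing a clarifying phrase, not a demonstrated breach.
- **The flow chart planned as Figure 1 may show exclusions by arm and reason.** Its content is not visible, so unequal removal might come to light there. But counts would not show what removal does to the estimate, and no planned analysis re-includes these patients.
- **The bone analysis could simply be declared a restricted, non-intention-to-treat population.** That would end the contradiction in wording, but it would leave the co-primary comparison conditioned on a post-randomisation event.

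**Conclusion.** The concern holds. The immobilisation exclusion contradicts the SAP's own intention-to-treat statement, and this follows from the text whatever the event rates. The missing time points are a lesser fault that could widen the problem. Under the assumed rates and effects shown, the distortion of the spine or hip comparison is about 0.01 to 0.05 SD in either direction, at most about half a standard error; its true size and sign cannot be known from the SAP. It concerns one secondary publication and leaves the AVC primary outcome untouched. It should be corrected, because the rule is wrong as written and the remedy is cheap.

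A minor editorial point: Table 1 of the bone publication has a row for prednisolone although users are excluded. That is an inconsistency in the table shell and not evidence of bias.

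**What to change.** - State that every exclusion in the bone publication refers to status at or before randomisation.
- Keep patients with later immobilisation, drug use or disease in the main Table 2 analysis as randomised. Those without a 24-month scan follow the missing-data rule already in the SAP.
- Present their removal only as a labelled sensitivity analysis, with counts by arm and reason. Use a definition of immobilisation written down in advance and applied blind to allocation.
- Reconcile the prednisolone row of Table 1 with the exclusion.

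The cost is a few lines of SAP wording, one extra supplementary table, and slightly noisier BMD changes from the retained patients.

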ACE denotes angiotensin-converting enzyme, ARB angiotensin-receptor blocker, AVC aortic valve calcification, dp-ucMGP dephosphorylated-uncarboxylated Matrix Gla-Protein, GFR glomerular filtration rate, NOAC new-onset anticoagulant † The body-mass index is the weight in kilograms divided by the square of the height in meters.

Table 2. Primary outcome and numerical secondary outcomes

Primary outcome and numerical secondary outcomes will be analyzed by mixed effects linear regression. The mixed effects linear regression models will include a fixed effect for treatment, a fixed effect for time point (baseline, 12 and 24 months) and a fixed effects interaction between treatment and time point. As baseline measurements are obtained before randomization, treatment at baseline will be modelled as a separate common treatment category, constraining baseline measurements to no systematic treatment effect between the two treatment arms, as suggested in literature (6). All mixed effects models will include a random intercept for each included patient. Normality assumptions on residuals and random effects will be evaluated by normal quantile-quantile plots. In case deviations from normality assumptions are detected analyses will be repeated with nonparametric bootstrapping with 1,000 bootstrapping samples (handling individual patients as bootstrapping clusters, and treatment groups as bootstrapping strata).

Due to the 12 primary outcome measures, we will apply the Bonferroni-Holm-method to adjust for multiple testing of these 12 p-values. The unadjusted p-values will be reported in the table, but it will be indicated by a * if treatment effects are still significant at the 5% level after Bonferroni-Holm-adjustment. No adjustment for multiple testing will be performed for secondary outcomes.

Missing data will be excluded from analyses in Table 2 (but see sensitivity analyses below).

	Vitamin K +D	Placebo		
	group	group		
	Mean change	Mean change	Treatment effect	P-value
	(95 % CI)	(95 % CI)	(95 % CI)	
Primary outcome				

Aortic calcification	0 – 24 months						
	0 – 24 months						
score							
Ascending							
• Arcus							
Descending							
 Suprarenal 							
 Infrarenal 							
 Renal artery 							
 Iliaca com artery 							
Iliaca ext artery							
Aortic diameter	0 – 24 months						
 Ascending 							
 Arcus 							
 Descending 							
 Infrarenal 							
Numerical secondary	Numerical secondary outcomes						
Aortic calcification	0 – 12 months						

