Primary and secondary numerical outcomes will be analyzed by mixed effects linear regression. The mixed effects linear regression models will include a fixed effect for treatment, a fixed effect for time point (baseline and 24 months) and a fixed effects interaction between treatment and time point. As baseline measurements are obtained before randomization, treatment at baseline will be modelled as a separate common treatment category, constraining baseline measurements to no systematic treatment effect between the two treatment arms, as suggested in literature (6). All mixed effects models will include a random intercept for each included patient. Normality assumptions on residuals and random effects will be evaluated by normal quantile-quantile plots. In case deviations from normality assumptions are detected analyses will be repeated with nonparametric bootstrapping with 1,000 bootstrapping samples (handling individual patients as bootstrapping clusters, and treatment groups as bootstrapping strata).

Missing data will be excluded from analyses in Table 2 (but see sensitivity analyses below).

Table 2 might be split into multiple tables in the resulting manuscript to ease dissemination.

		Vitamin K +D	Placebo		
		group			
		Mean change	group Mean change	Treatment effect	P-value
		(95 % CI)	Mean change (95 % CI)	(95 % CI)	r-value
Primary outcomes		(33 % CI)	(33 /0 CI)	(33 /0 CI)	1
Volumetric BMD in	0 – 24 months				
spine	0 – 24 months				
Volumetric BMD in	0 – 24 months				
hip	0 – 24 months				
Secondary outcomes					
Volumetric bone minera	I density (mg/cm3)				
voidifietric borie miliera	ruensity (mg/cms)				
Trabeculært vBMD	0 – 24 months				
total hip					
Trabeculært vBMD	0 – 24 months				
femoral neck					
Trabeculært vBMD	0 – 24 months				
inter-trochanteric					
regions					
Trabeculært vBMD	0 – 24 months				
sub-trochancheric					
regions					
Cortical vBMD total	0 – 24 months				
hip					
Cortical vBMD	0 – 24 months				
femoral neck					
Cortical vBMD inter-	0 – 24 months				
trochanteric regions					
Cortical vBMD sub-	0 – 24 months				
trochancheric					
regions					
Bone geometry (cm2)		1			1
Trabecular area sub-	0 – 24 months				
trochancheric					
regions					
Trabecular area	0 – 24 months				
femoral neck					
Trabecular area	0 – 24 months				
inter-trochanteric					
regions					
Trabecular area sub-	0 – 24 months				
trochancheric					
regions					
Cortical area sub-	0 – 24 months				
trochancheric					
regions					

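### The bone publication tests two co-primary outcomes, spine and hip BMD, each at 0.05 with no adjustment and no rule for claiming success; if either alone suffices, the false-claim rate is up to 9.75%

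*SAP*

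**What the plan says.** In the bone publication, under Outcomes, the SAP lists two primary outcomes: "Co-primary outcome 1: change in BMD in spine from baseline to 24 month (numerical") and "Co-primary outcome 1: change in BMD in hip from baseline to 24 month (numerical"). Both are numbered 1, so the numbering gives no order.

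Table 2 (Main analyses) of the same section states that "Primary and secondary numerical outcomes will be analyzed by mixed effects linear regression". The table shell places spine and hip together under the primary heading, each with its own treatment effect, confidence interval and p-value. The text on Table 2 says nothing about multiplicity or about what counts as success.

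The threshold comes from Statistical principles: "Two-sided p-values of 0.05 or less were considered to indicate statistical significance". That section also says "All analyses were performed in the intention-to-treat population and as superiority analyses", and it adds no rule for several primary outcomes.

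The aortic publication is the only other one with outcomes labelled co-primary; its second is "Co-primary outcome 2: change in aortic dilatation (numerical) from baseline to 24 month". Its Table 2 text matches the bone text closely but adds a multiplicity paragraph: "Due to the 12 primary outcome measures, we will apply the Bonferroni-Holm-method to adjust for multiple testing of these 12 p-values". Unadjusted p-values are shown there, and "it will be indicated by a * if treatment effects are still significant at the 5% level after Bonferroni-Holm-adjustment". Secondary outcomes are expressly left unadjusted.

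**The concern.** With two primary outcomes, a plan has to say what counts as a positive primary result. The usual choices are that either outcome suffices (with the error rate controlled across the two), that both are required, or that they are tested in a fixed order. The bone section makes none of these choices.

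Suppose spine gives p = 0.03 and hip p = 0.20. As written, this could be presented as a positive primary finding at the spine or as a primary hypothesis that was not supported. The plan leaves that open until after the results are known, which is what prespecification should prevent.

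The two readings also carry different error rates. If either site is enough, each test keeps its own 5% level but the chance of at least one false primary claim exceeds 5%. If both are required there is no inflation, and the cost falls on power.

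**Working it through.** **Inputs.** Two primary tests (bone publication, Outcomes and Table 2), each two-sided at 0.05 (Statistical principles). The SAP states no error rate across the two tests and no power for BMD, so there is no figure of its own to reproduce. It gives no spine-hip correlation either. The correlation r between the two test statistics is therefore assumed, over the range 0 to 0.9, and the statistics are taken as jointly normal.

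**Either site suffices, no adjustment, no true effect at either site.** The chance of at least one false claim is 1 − P(|Z₁| < 1.960 and |Z₂| < 1.960). At r = 0 this is 1 − 0.95² = 1 − 0.9025 = 0.0975.

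**Bonferroni-Holm.** When neither site has an effect, a false claim requires the smaller p-value to pass 0.025 (critical value 2.241). At r = 0 this is 1 − 0.975² = 0.0494.

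**Both sites required at 0.05.** By inclusion-exclusion, P(both) = 0.05 + 0.05 − P(at least one). At r = 0 this is 0.10 − 0.0975 = 0.0025.

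| Assumed r | Either, unadjusted | Either, Holm | Both required |
|---|---|---|---|
| 0 | 9.75% | 4.94% | 0.25% |
| 0.3 | 9.51% | 4.84% | 0.49% |
| 0.5 | 9.07% | 4.65% | 0.93% |
| 0.7 | 8.35% | 4.30% | 1.65% |
| 0.9 | 7.04% | 3.62% | 2.96% |

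For jointly normal two-sided tests, 9.75% is the maximum at any correlation, negative ones included. With no assumption on the joint distribution the bound is 0.05 + 0.05 = 10%. The both-required column assumes no effect at either site. If one site has a large true effect, the rate of false joint claims approaches 5% but does not exceed it.

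**Power, for illustration only.** Assume 80% power per site at 0.05, that is, a non-centrality of 1.960 + 0.842 = 2.80.

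- At level 0.025 the power for one site is Φ(2.80 − 2.241) ≈ 0.712. This is essentially the Holm power for a site when the other has no effect (71%).
- If both sites have this effect, Holm also rejects a site with p between 0.025 and 0.05 when the other has p ≤ 0.025. At r = 0 the per-site power is 0.712 + (0.80 − 0.712) × 0.712 ≈ 0.775. At r = 0.9 it is 0.751.
- If both sites are required at 0.05, the power to claim is 0.80² = 0.64 at r = 0 and 0.75 at r = 0.9.

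**The case against.** The strongest reply is that no inflation has been shown. Co-primary often means that both outcomes must succeed, and then no adjustment is needed. The 9.75% needs both the either-one reading and zero correlation, although spine and hip are measured in the same patients. This is right as far as it goes: the inflation is conditional, and 9.75% is an upper figure. But the SAP does not say that both are required. In the aortic section the same label goes with marking each surviving effect on its own, so the either-one reading is plausible for bone. Even at a correlation of 0.9 that reading gives 7.0%.

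A second reply is that the aortic rule does not bind the bone section, because the reason given there is the number of measures, 12, and not the co-primary label. That stands. The difference between the two sections is unexplained, but it is not a breach of a rule the SAP sets itself.

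A third reply is that Table 2 can be read as two separate claims, each at 5%, with both p-values on display so that readers can adjust for themselves. Familywise control is indeed partly a matter of choice, and showing both sites limits selective reporting. But the SAP does not say that separate claims are intended, and display does not settle what may be called a positive primary result.

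Finally, this is a secondary publication, and the sample size section covers only aortic valve calcification. That limits the weight of the point without removing it.

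**Conclusion.** The concern holds. The definite defect is that the bone section names two primary outcomes without a claim rule, a testing order or an adjustment. The size of the consequence depends on the reading. If either site suffices, the chance of a false primary claim with no true effect is 9.75% at correlation 0, 9.1% at 0.5 and 7.0% at 0.9, assuming jointly normal test statistics. If both must succeed it never exceeds 5%, and what remains is the missing statement. The point should be corrected. It affects how the bone publication may be interpreted, not the trial's main conclusion.

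**What to change.** State one rule in the bone section before the BMD data are analysed by treatment group. Either would do:

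1. **Either site can support a claim.** Apply Bonferroni-Holm to the two primary BMD p-values, report them unadjusted, and mark with * the effects still significant at 5% after adjustment. This matches the aortic Table 2.
2. **Both sites are required.** State that the primary hypothesis is supported only if spine and hip are each significant at 0.05. No adjustment is then needed.

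As an editorial correction, number hip as co-primary outcome 2.

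The change is one sentence, with no new data or model. On the illustrative assumption of 80% power per site, option 1 lowers power for a given site to about 71% if the other site has no effect, and to between 75% and 77.5% if both have this effect. Option 2 gives 64% to 75% power to claim, over correlations 0 to 0.9.
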